RV 397 Statistical Analysis Plan

Safety and Therapeutic Efficacy of the Broadly Neutralizing HIV-1 Specific Monoclonal Antibody VRC01 during Analytic Treatment Interruption in Patients who Initiated Antiretroviral Therapy During Early Acute HIV Infection

Study Agent Provided by
Vaccine Research Center/NIAID/NIH, Bethesda, MD

Study Conducted By
U.S. Military HIV Research Program, [name]
The Thai Red Cross AIDS Research Center, Bangkok, Thailand

In Collaboration with
Vaccine Research Center, NIAID, NIH

Study Sponsored By
National Institute of Allergy and Infectious Diseases (NIAID), Division of AIDS (DAIDS), National Institutes of Health (NIH)
Bethesda, Maryland

IND Number: 126,001

DAIDS-ES ID: 12001

Protocol Chair:
Local Principal Investigator:
Project Leader (USA):
Project Leader (Thailand):
DoD Research Monitor:
DAIDS Medical Officer:

[name], PhD
[name], PhD
[name]
[name], MPH
[name]
[name]

STATISTICAL ANALYSIS PLAN

Baseline characteristics including demographics and laboratory measurements will be summarized using descriptive statistics.

The analysis of study data will be primarily descriptive, with emphasis on tabular and graphical displays. Summary statistics will be calculated, along with point and interval estimates of solicited and unsolicited adverse event and immune response rates. This study is exploratory, and any statistical inferences will be hypothesis generating, and not confirming.

1 Primary Endpoints

The primary efficacy endpoint is sustained virologic control (HIV RNA <50 copies/mL) at 24 weeks after ATI. The rate of virologic control will be compared between treatment groups using a two-sided exact unconditional test with a significance level of 0.05.

To assess safety, summaries of the number and percentage of subjects experiencing any SAE, AE, or reactogenicity will be tallied by treatment group and presented along with two-sided exact 95% confidence intervals for the proportion.

For solicited AEs/reactogenicity, number and percentage of subjects experiencing each type of solicited sign or symptom will be tabulated by severity. For a given sign or symptom, each subject's solicited AEs will be counted once under the maximum severity for all assessments.

For unsolicited AEs, number and percentages of participants experiencing each specific adverse event will be tabulated by severity and relationship to treatment. For the calculations in these tables, each participant's adverse experience will be counted once under the maximum severity or strongest recorded causal relationship to treatment.

Further, frequency of solicited and unsolicited adverse events will be reported (together and separately) by system organ class, preferred term, and treatment group overall and at various timepoints throughout the study.

A complete listing of adverse experiences for each participant will provide details including severity, relationship to treatment type, onset, duration and outcome.

2 Secondary Endpoints

1. Time to viral rebound and level of rebound viremia after cessation of ART.

Time to viral load rebound will be described using a Kaplan-Meier estimator to account for possible censoring and compared between treatment groups using an exact log-rank test. Number of HIV RNA copies at the time of rebound viremia will be described using medians and range and compared between treatment groups using a Wilcoxon-Rank Sum test.

2. Time to ART resumption for any reason after cessation of ART

Time to ART resumption will be described using a Kaplan-Meier estimator to account for possible censoring and compared between treatment groups using an exact log-rank test.

3. Detectable HIV RNA via single copy assay at various timepoints, such as weeks 24 and 48, as compared to baseline at week 0.

Number of HIV RNA copies will be described using medians and range at baseline, week 24, and week 48 for subjects with HIV RNA <50 copies/mL by standard PCR. Change from baseline at week 24 and week 48 will be compared between treatment groups using a Wilcoxon-Rank Sum test.

4. CD4+ T cell count various timepoints, such as weeks 24 and 48, as compared to baseline at week 0. CD4+ T cell counts will be described using medians and range at baseline, week 24, and week 48. Change from baseline at week 24 and week 48 will be compared between treatment groups using a Wilcoxon-Rank Sum test.

5. Cell-associated HIV RNA and DNA in the peripheral compartment various timepoints, such as weeks 24 and 48, as compared to baseline at week 0. Cell-associated HIV RNA and DNA in the peripheral compartment will be described using medians and range at baseline, week 24, and week 48. Change from baseline at week 24 and week 48 will be compared between treatment groups using a Wilcoxon-Rank Sum test.

6. Neuropsychological battery performance at weeks 24 and 48, as compared to baseline at week 0. Neuropsychological data will be summarized using z-scores based on age-matched normative data when such data is available or as raw scores when not available. With either approach, individual performance can be compared longitudinally to determine the impact of the intervention on cognitive performance, the primary interest of the neuropsychological testing portion of this study.

7. Frequency of hospitalization and incidence of non-AIDS related conditions.

Frequency of hospitalizations will be summarized and described by treatment group, Number of hospitalizations can be compared between groups using a Wilcoxon-Rank Sum test and proportion of subjects experiencing a hospitalization will be compared using an exact unconditional test. Incidence of non-AIDS related conditions will be compared in a similar fashion.

Exploratory objectives will be analyzed in a similar fashion to primary and secondary objectives although if the rate of consent for invasive procedures is low then analyses may be primarily descriptive. Continuous variables will be described at each timepoint using medians and range. Change from baseline will be compared between treatment groups at weeks 24 and 48 using Wilcoxon-Rank Sum tests. If possible repeated measures models will be fit to account for within subject correlation and assess a treatment group effect. Binary endpoints will be compared between treatment groups using exact unconditional tests. Clinical characteristics will be summarized and described by treatment groups. Significance will be assessed using two-sided testing at the 0.05 level. Given the size and exploratory nature of the trial, adjustments for multiple comparisons will not be made.

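### The single-copy subset in secondary item 3 can pool participants controlling off ART with participants suppressed on resumed ART; the primary endpoint leaves a narrower scoring question of the same kind

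*SAP*

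**What the plan says.** **Item 3 (SAP, 2 Secondary Endpoints).** Single-copy HIV RNA is described by median and range "at baseline, week 24, and week 48 for subjects with HIV RNA <50 copies/mL by standard PCR". Change from baseline to weeks 24 and 48 is then compared between treatment groups with a Wilcoxon rank sum test. The only entry condition is the standard-PCR result.

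**Primary endpoint (SAP, 1 Primary Endpoints).** "The primary efficacy endpoint is sustained virologic control (HIV RNA <50 copies/mL) at 24 weeks after ATI". On how the groups are then tested against each other, the section adds: "The rate of virologic control will be compared between treatment groups using a two-sided exact unconditional test with a significance level of 0.05".

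**Related text.** The title places efficacy in the interruption period: "Therapeutic Efficacy of the Broadly Neutralizing HIV-1 Specific Monoclonal Antibody VRC01 during Analytic Treatment Interruption". Item 1 covers rebound: "Time to viral load rebound will be described using a Kaplan-Meier estimator to account for possible censoring". Item 2 is a separate endpoint: "Time to ART resumption for any reason after cessation of ART". No section links ART resumption to the primary endpoint or to the item 3 subset.

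**The concern.** The trial studies what happens to the virus while ART is stopped. A plasma HIV RNA below 50 copies/mL at week 24 or 48 can arise in two ways: the participant is controlling virus without ART, or has gone back on ART and is suppressed by it. Item 2 shows that the SAP expects ART to be resumed and allows for any reason.

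In item 3 both kinds of participant meet the entry rule. A low single-copy value, or a small change from baseline, may then reflect renewed ART, and neither the planned summary nor the single test shows which. The groups may also differ in how many of their subset members are on ART, so a difference, or the lack of one, has no clear meaning for control off ART.

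The primary endpoint raises a narrower version. Someone who resumes ART while still below 50 copies/mL can stay below it throughout and so meet the literal criterion. If the groups are small, how one such person is scored can decide whether the primary test crosses 0.05.

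**Working it through.** **1. Who meets each rule as written.** The rules were set against the possible courses after ART is stopped.

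| Course | Item 3 subset at the visit | Primary endpoint, read literally |
|---|---|---|
| Off ART, always <50 copies/mL | in | success |
| Rebounded, still ≥50 copies/mL at the visit | out | not success |
| Rebounded, resumed ART, <50 copies/mL again | in | not success, because control was not sustained |
| Resumed ART before week 24 without rebound, always <50 copies/mL | in | success |

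Two on-ART courses enter item 3, but only one reaches the primary endpoint. The difference is the word for lasting control in Section 1, which item 3 lacks. The time reference in Section 1 fixes the origin of the 24 weeks; it does not state ART status at their end.

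**2. Possible make-up of the item 3 subset.** The SAP gives no figure to reproduce. Assumptions: 10 per group; 2 and 0 participants controlling off ART; a share s of the others (8 and 10) back on ART and suppressed. Subset size = off-ART controllers + s × others.

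| s | First group | Second group | On ART in subset |
|---|---|---|---|
| 0 | 2 + 0 = 2 | 0 + 0 = 0 | 0 of 2; subset empty |
| 0.5 | 2 + 0.5 × 8 = 6 | 0 + 0.5 × 10 = 5 | 4 of 6; 5 of 5 |
| 1 | 2 + 8 = 10 | 0 + 10 = 10 | 8 of 10; 10 of 10 |

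In the last two rows the Wilcoxon test mostly compares people on ART. In the first row there is nobody to compare. The shares are invented to show the range; they are not forecasts.

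**3. Sensitivity of the primary test, illustration only.** The SAP does not say which exact unconditional test it means, so three were run, all two-sided: Barnard pooled, Barnard unpooled and Boschloo. One participant who resumed without rebound is scored as a success in the group that otherwise has 0. Ranges are over the three statistics.

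| Assumed sizes | Successes | p without that success | p with it |
|---|---|---|---|
| 10/10 | 3 vs 0, then 3 vs 1 | 0.088–0.116 | 0.330 |
| 10/10 | 4 vs 0, then 4 vs 1 | 0.042 | 0.151 |
| 10/10 | 5 vs 0, then 5 vs 1 | 0.013 | 0.062 |
| 10/10 | 6 vs 0, then 6 vs 1 | 0.004 | 0.023 |
| 15/5 | 8 vs 0, then 8 vs 1 | 0.031–0.045 | 0.252–0.338 |
| 15/5 | 10 vs 0, then 10 vs 1 | 0.009–0.021 | 0.093–0.150 |
| 15/5 | 11 vs 0, then 11 vs 1 | 0.004–0.005 | 0.0501–0.1005 |

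At 10/10 only 4 and 5 cross 0.05, out of all counts from 1 to 10. At 15/5, counts of 8 to 11 cross under all three statistics (11 only just under the pooled one, at 0.0501), and 7 and 12 under one only. If the extra success falls in the higher group, the move is the other way: at 10/10 only 3 vs 0 becoming 4 vs 0 crosses (0.088–0.116 to 0.042).

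**The case against.** **The context already means off-ART control.** The title, the requirement that control last, and the counting from interruption all point that way, and an analyst would have to read against them to score a participant on ART as a success. A short SAP may also leave the operational definition to the protocol. This largely stands for the primary endpoint. It reduces that limb to a clarification, although scoring an event that the plan itself foresees is normally settled in the SAP.

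**The p-value examples show small-sample fragility.** In any trial of about 20, moving one participant near the threshold can change the result. This stands. Sizes and counts are assumed, most counts at 10/10 do not cross, and the SAP treats all inference as exploratory.

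**Item 3 may be limited to low-level samples because that is where a single-copy assay is informative.** That is a reasonable purpose, and the SAP never presents item 3 as evidence of off-ART control. It does not remove the problem: the table as planned cannot tell the two kinds of participant apart.

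**A split by ART status conditions on another post-baseline outcome.** This is correct. The split can describe who is in the subset; it cannot repair the between-group comparison.

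**What a reader might infer, without support.** One might conclude that the primary endpoint counts participants who rebounded and were re-suppressed on ART as successes. The requirement of lasting control excludes them. One might also treat the two gaps as identical; item 3's affected set is wider. Nor does the SAP show that anyone will resume ART without rebound, or that the primary result will be wrong.

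**Conclusion.** The item 3 limb holds on the wording alone. Followed exactly, the rule pools participants off ART with participants suppressed or re-suppressed on resumed ART, and one test compares the mixture. How large the mixture is cannot be known from the SAP; under the assumptions shown it ranges from nobody to most of the subset.

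The primary limb holds only narrowly: resumption before week 24, without rebound, and only if the protocol does not already define control as off ART.

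Overall severity is low. The fixed-week comparisons in items 4 and 5 are not affected; they are legitimate comparisons whatever treatment has been resumed. The point concerns scoring and reporting only, not when ART is resumed.

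**What to change.** **Item 3.** Report single-copy results in the subset by treatment group and by ART status at the visit, with the number of participants in each cell. Label the split as descriptive, because ART status is a post-baseline outcome. State that the pooled Wilcoxon test is not to be read as evidence of control off ART.

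**Section 1.** Unless the protocol already does so, add a sentence: success means HIV RNA below 50 copies/mL through week 24 while off ART, and ART resumption for any reason before week 24 is scored as not in control. List the reasons for resumption by group. Other scoring choices are possible; what matters is that one is fixed before the data are seen.

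**Cost.** One sentence, one listing and one split table, all from the ART dates that item 2 already needs. Resumption for non-virologic reasons would count as failure, which may slightly lower the control rate; the listing makes this visible. Cells in the split table may be very small.

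### The single-copy-assay endpoint is named as detectability, but its analysis reports copy number in a suppressed subset and compares no proportion detectable

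*SAP*

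**What the plan says.** SAP section 2 (Secondary Endpoints), item 3, names the endpoint: "Detectable HIV RNA via single copy assay at various timepoints", with weeks 24 and 48 as examples and week 0 as the baseline for comparison. The analysis text below it has two parts.

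- The summary: "Number of HIV RNA copies will be described using medians and range at baseline, week 24, and week 48", limited to a subset, "for subjects with HIV RNA <50 copies/mL by standard PCR".
- The comparison: "Change from baseline at week 24 and week 48 will be compared between treatment groups using a Wilcoxon-Rank Sum test". This sentence does not repeat the restriction.

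Two other places bear on the point. Item 7 of the same section names a test for its own proportion: "proportion of subjects experiencing a hospitalization will be compared using an exact unconditional test". The closing paragraph, which begins "Exploratory objectives will be analyzed in a similar fashion to primary and secondary objectives", also states: "Binary endpoints will be compared between treatment groups using exact unconditional tests".

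**The concern.** The endpoint name asks whether RNA can be detected by an assay more sensitive than standard PCR. The analysis asks how far copy number has moved, and its summary covers only those already below the standard-PCR threshold. A programmer who follows item 3 would produce medians, ranges and a Wilcoxon p-value, and would never tabulate how many participants in each arm were detectable.

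The restriction matters separately. At weeks 24 and 48, being below 50 copies/mL is an outcome of treatment and not a baseline characteristic. If the arms differ in how many participants stay suppressed, the subset holds different kinds of participants in each arm. A difference in copy number, or the lack of one, could then come from that selection. The participants who failed most clearly on the named endpoint are the ones removed.

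**Working it through.** No arithmetic applies to the main point. The SAP gives no arm sizes, detectability rate or assay limit, and there is no stated figure to reproduce. The check sets the texts side by side.

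1. **Name against analysis.** The name in item 3 is a state, detectable or not. The variable analysed is a count of copies and its change from week 0. Item 3 contains no proportion, no denominator for one and no test of one.

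2. **How the SAP treats proportions elsewhere.** The primary endpoint in section 1 is a rate of virologic control, and it is assigned a two-sided exact unconditional test at 0.05. Item 7 has both a count and a proportion: the count gets a Wilcoxon test and the proportion an exact unconditional test. Item 3 gets only the count-type analysis, in the form used for CD4 count (item 4) and cell-associated RNA and DNA (item 5).

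3. **The restriction against the primary endpoint.** Section 1 defines primary success as sustained control below 50 copies/mL at 24 weeks after treatment interruption. Item 3 restricts its summary by the same threshold at week 24. If week 24 is counted from the interruption, membership of the subset largely repeats primary success. The two are not identical, because the primary requires sustained control and item 3 does not require participants to be off ART. Item 2 makes ART resumption an endpoint, so resumption is foreseen. Someone re-suppressed on ART at the visit would fall inside the item 3 subset as written.

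4. **Reach of the restriction.** It is attached to the descriptive sentence. If it also governs the test, the test compares selected groups. If it does not, the test covers a different set from the summary beside it, and that set is not stated. Either way the text needs repair.

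5. **Undetectable results.** Item 3 gives no detection limit and no rule for entering an undetectable single-copy result into a median, a range or a change score. A participant undetectable at both visits has no measured change.

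**The case against.** The strongest reply is that item 3 was meant as a quantitative endpoint all along. The SAP never calls it binary. Its name has the same form as items 4 and 5, which are plainly quantitative, and comparison with baseline suits a measured amount. Limiting a sensitive assay to samples below the standard-PCR threshold is also sensible laboratory practice, and rebounders are covered by the primary endpoint and by item 1. This much stands: that the endpoint is binary is inferred from the word detectable, and a copy-number summary in the subset is reasonable as description. It does not remove the mismatch between name and analysis, or justify comparing arms within a subset selected after baseline.

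A reader might infer two stronger claims that the SAP does not support.

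- **That detectability is certain never to be tested.** The sentence on binary endpoints in the closing paragraph of section 2 could be read as trial-wide, since that paragraph also carries the significance level and the multiplicity statement. The plainer reading confines it to exploratory objectives. If it is trial-wide, item 3 omits an analysis that the SAP requires. If it is not, detectability has no assigned test.

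- **That the suppressed subset is bound to be too small to compare.** This depends wholly on assumptions. With arm sizes n1 and n2 and proportions p1 and p2 below 50 copies/mL, the chance that at least one arm of the subset is empty is 1 − [1 − (1 − p1)^n1] × [1 − (1 − p2)^n2]. Assume 12 against 6 participants. At 30% against 5% this is 1 − (1 − 0.0138) × (1 − 0.7351) = 74%. At 70% against 50%, as could happen if participants re-suppressed on ART enter the subset, it is 1 − (1 − 0.0000005) × (1 − 0.0156) = 1.6%. The SAP supplies none of these inputs, so no such percentage can support the point.

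**Conclusion.** The point holds as a mismatch. Item 3 names detectability, and its own text neither reports nor compares it. The copy-number summary at weeks 24 and 48 is conditioned on a post-baseline result that overlaps the primary endpoint and leaves out participants who are plainly detectable. That the same condition limits the Wilcoxon test is probable but not stated.

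The conclusion rests on the wording of the SAP and on reading detectable in its ordinary sense; no numerical size can be given. Severity is modest, since the endpoint is secondary and section 1 is preceded by a statement that the study is exploratory and its inferences hypothesis generating. The change is still worth making, because a named secondary endpoint should have an analysis that answers it.

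**What to change.** Rewrite the analysis text of item 3 as follows.

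- **Comparison.** At weeks 24 and 48, compare between arms the proportion of all assigned participants with detectable RNA by single copy assay. Count a standard-PCR result of 50 copies/mL or more as detectable. Use the exact unconditional test that the SAP already applies to proportions, with a confidence interval for the difference. State the assay limit, and tabulate the week 0 proportions beside the later ones.
- **ART resumption.** In this analysis, score participants who have resumed ART by the visit as not maintaining undetectability, and show them separately. Without this rule, anyone re-suppressed on ART would count as undetectable and the comparison would mix treated with untreated suppression.
- **Copy number.** Keep it as a descriptive summary among those below 50 copies/mL, with non-detects shown as below the assay limit.

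The cost is one rewritten paragraph and no new assays. There are two downsides: the variable partly overlaps the primary endpoint at week 24, and differences in copy number within the suppressed subset would be described but not tested.

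### CD4 (secondary item 4) is compared only by an unadjusted rank test on change; a baseline-adjusted difference with a 95% CI would be a cheap supportive addition

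*SAP*

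**What the plan says.** SAP section 2 (Secondary Endpoints), item 4 sets the endpoint as "CD4+ T cell count various timepoints, such as weeks 24 and 48, as compared to baseline at week 0". The description is "CD4+ T cell counts will be described using medians and range at baseline, week 24, and week 48", and the comparison is "Change from baseline at week 24 and week 48 will be compared between treatment groups using a Wilcoxon-Rank Sum test". The last sentence also stands in items 3 and 5; the point here is its use in item 4. Item 4 names no effect estimate, no interval and no covariate.

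Two other places bear on this:

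- The opening paragraphs promise summary statistics "along with point and interval estimates of solicited and unsolicited adverse event and immune response rates". These intervals are for rates, not for a difference in CD4 count. The same paragraphs say: "This study is exploratory, and any statistical inferences will be hypothesis generating, and not confirming".
- The closing paragraph of section 2, on exploratory objectives, adds: "If possible repeated measures models will be fit to account for within subject correlation and assess a treatment group effect". It names no baseline covariate and no interval.

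**The concern.** As item 4 stands, the only between-group CD4 result that it specifies is a p-value at each of two visits. In a small trial, a non-significant p-value without an interval cannot separate absence of a meaningful CD4 difference from too few participants to tell. For a study whose stated purpose is description and hypothesis generation, the estimate and its uncertainty are the more useful output. This reporting argument needs no assumed sample size or correlation.

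The second strand is precision. Week 0 CD4 is collected, but subtracting it fixes the baseline slope at 1. When the baseline/follow-up correlation is low to moderate, that adds noise and leaves the comparison sensitive to chance baseline imbalance. At stake is some efficiency and clarity on one secondary endpoint, nothing more.

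**Working it through.** **Inputs from the SAP.** CD4 at weeks 0, 24 and 48; "Significance will be assessed using two-sided testing at the 0.05 level". The SAP gives no sample size, allocation, CD4 standard deviation, effect size or rho, so there is no figure of its own to reproduce.

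**Assumed inputs.** Total N = 20, with 12 and 40 for range; arms of 10/10 and 15/5; rho 0.3 to 0.85; equal SD at baseline and follow-up; a true shift of 1 SD for power; normal data, or a t distribution with 3 df for heavy tails; an exact Wilcoxon test. Simulations used 20,000 trials per power scenario and 40,000 per normal null scenario.

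**1. Variance ratio, ANCOVA to change score.** With k = 1/n1 + 1/n2:

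- Change score: 2σ²(1 − rho)k
- ANCOVA: σ²(1 − rho²)k × (1 + 1/(N − 4))
- Ratio: (1 + rho)/2 × (1 + 1/(N − 4))

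At N = 20 the factor is 1 + 1/16 = 1.0625. This gives 0.65 × 1.0625 = 0.69, 0.75 × 1.0625 = 0.80, 0.85 × 1.0625 = 0.90 and 0.925 × 1.0625 = 0.98 at rho 0.3, 0.5, 0.7 and 0.85. Simulated ratios at 10/10 agree.

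| N | rho 0.3 | rho 0.5 | rho 0.7 | break-even rho |
|---|---|---|---|---|
| 12 | 0.73 | 0.84 | 0.96 | 0.78 |
| 20 | 0.69 | 0.80 | 0.90 | 0.88 |
| 40 | 0.67 | 0.77 | 0.87 | 0.95 |

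Break-even is 2/(1 + 1/(N − 4)) − 1. Above it, adjustment costs precision.

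**2. Is the planned test valid?** On normal null data the Wilcoxon test on change rejected 4.1% to 4.4% of the time and ANCOVA 4.9% to 5.2%. Both hold the 5% level.

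**3. Power at N = 20, 10/10, 1 SD shift, normal data.**

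| rho | Wilcoxon on change | t-test on change | ANCOVA |
|---|---|---|---|
| 0.3 | 39% | 43% | 57% |
| 0.5 | 51% | 56% | 66% |
| 0.7 | 74% | 78% | 82% |
| 0.85 | 96% | 97% | 97% |

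The middle column matters: 24%, 33%, 55% and 92% of the Wilcoxon-to-ANCOVA gap (from unrounded powers) comes from leaving the rank test, not from adjusting for baseline.

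**4. Mean 95% CI width at 10/10, as a ratio.**

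| Comparison | rho 0.3 | 0.5 | 0.7 | 0.85 |
|---|---|---|---|---|
| ANCOVA / t interval on change, normal | 0.83 | 0.89 | 0.95 | 0.99 |
| ANCOVA / Hodges-Lehmann on change, normal | 0.78 | 0.84 | 0.90 | 0.93 |
| ANCOVA / Hodges-Lehmann on change, heavy tails | 0.88 | 0.95 | 1.03 | 1.09 |

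The first row isolates baseline adjustment. With heavy tails the Hodges-Lehmann interval is narrower from about rho 0.7. Coverage with normal data is 94.9% to 95.1% for ANCOVA and 95.6% to 95.9% for Hodges-Lehmann.

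**5. Chance imbalance, if groups are randomised.** The baseline mean difference has SD √(1/10 + 1/10) = 0.447 at 10/10 and √(1/15 + 1/5) = 0.516 at 15/5. A gap of 0.5 SD or more therefore occurs in 26% and 33% of trials. A gap of 0.5 SD shifts the expected change-score difference by (1 − rho) × 0.5, which is 0.25 SD at rho 0.5. Among such imbalanced trials, the Wilcoxon test on change rejects a true null about 8% (10/10) and 7% (15/5) of the time at rho 0.5, while ANCOVA stays near 5%.

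**The case against.** The strongest reply is that nothing here is wrong. The test holds its level, the endpoint is secondary, and the SAP favours exact and rank methods throughout, which suits a trial that forgoes multiplicity adjustment "Given the size and exploratory nature of the trial, adjustments for multiple comparisons will not be made". ANCOVA brings a linearity assumption, targets a mean difference where item 4 describes medians, and may disagree with the Wilcoxon result. The gain rests wholly on assumed inputs, and part of the power gap has nothing to do with baseline. The inflated rejection rates apply only to trials selected for imbalance. A Hodges-Lehmann interval alone would supply a CI that matches the planned test.

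Most of this stands, and it limits the point to an optional addition. It does not defeat an addition that removes nothing, provided the Wilcoxon test is named as the planned comparison. Hodges-Lehmann meets the reporting need but does not use baseline beyond subtraction, so the two can stand together.

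Two extensions that a reader might infer are not supported:

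- **Adding baseline as a covariate to the exploratory repeated measures models.** Those models are conditional and unspecified. A version that keeps week 0 as an outcome should not also take it as a covariate, and the exploratory endpoints may include assays limited by a detection floor.
- **Extending the suggestion to items 3 and 5.** These share the comparison sentence, but single copy and cell-associated HIV measurements can be floor-limited, and a rank analysis is reasonable there.

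**Conclusion.** The point holds as a cheap improvement to a valid plan. A reader might infer that the Wilcoxon test on change is an error, or that ANCOVA would always be more precise; the SAP supports neither. The missing difference and CI are plain from item 4, and would remain missing even if the conditional repeated measures sentence were read as reaching CD4.

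The precision gain is conditional. At an assumed N of 20 with normal data, it is a variance reduction of about 31%, 20% and 10% at rho 0.3, 0.5 and 0.7, and almost nothing at 0.85 or above. With heavy tails it can reverse from about rho 0.7. The imbalance argument needs randomised groups, which this SAP does not state. Calling the test valid assumes comparable groups and no informative missing data. The primary conclusion is not affected.

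**What to change.** Keep the Wilcoxon rank-sum test on change as the planned comparison for item 4. Add one sentence: as a supportive estimate, the between-group difference in CD4 count at weeks 24 and 48 will be reported with a 95% CI from ANCOVA with week 0 CD4 as covariate. Optionally, report a Hodges-Lehmann difference with CI beside the Wilcoxon test, which is sensible because rho and the distribution are unknown. Leave items 3 and 5, other floor-limited assays and the exploratory repeated measures models as planned.

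The cost is a sentence or two, minor programming and no new data. The downsides are one degree of freedom, a linearity assumption, and a second result that may differ from the Wilcoxon test; the text should say that the latter remains the planned test. Naming the covariate in the SAP also avoids choosing it after seeing the data.

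### Secondary endpoint 6 (neuropsychological performance) states no comparison between treatment groups and relies on within-person change, which cannot separate the intervention's effect from retest learning and time

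*SAP*

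**What the plan says.** SAP section 2 (Secondary Endpoints), item 6, defines the endpoint as "Neuropsychological battery performance at weeks 24 and 48, as compared to baseline at week 0". Scores are to be summarised as age-matched z-scores where norms exist and as raw scores where they do not. On either scale, the item continues, "individual performance can be compared longitudinally to determine the impact of the intervention on cognitive performance", and it calls this "the primary interest of the neuropsychological testing portion of this study". It gives no test and does not mention treatment groups.

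Items 3, 4 and 5 use the same timepoints and the same baseline, and each ends with the sentence "Change from baseline at week 24 and week 48 will be compared between treatment groups using a Wilcoxon-Rank Sum test". Items 1 and 2 compare groups by exact log-rank test, and item 1 adds a rank-sum test. Item 7 states "Number of hospitalizations can be compared between groups using a Wilcoxon-Rank Sum test" and adds an exact unconditional test for proportions.

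The closing paragraph of section 2 begins "Exploratory objectives will be analyzed in a similar fashion to primary and secondary objectives". Further on it says "Change from baseline will be compared between treatment groups at weeks 24 and 48 using Wilcoxon-Rank Sum tests", and it allows repeated measures models with a treatment group effect where possible. The SAP's introduction says that "any statistical inferences will be hypothesis generating, and not confirming".

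**The concern.** Item 6 does more than leave a test unspecified. It states an inference: that following individuals over time can show what the intervention did to cognition. Change within a person from week 0 contains at least four components:

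- any effect of VRC01;
- learning from taking the battery again at weeks 24 and 48;
- other changes over time;
- the effect of interrupting or resuming ART.

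A within-person comparison observes only their sum. Norms matched on age adjust for age, and nothing in the item says that they adjust for repeat testing. Raw scores adjust for neither.

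The error can go in either direction. An improvement produced by practice could be reported as a benefit of the intervention, or practice gain could hide a real decline. The SAP already has treatment groups, and comparing change between them removes whatever the groups share.

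**Working it through.** **1. The items side by side**

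| Secondary item | Comparison between treatment groups stated? | Method |
|---|---|---|
| 1 Viral rebound | Yes | Exact log-rank; rank-sum for level |
| 2 ART resumption | Yes | Exact log-rank |
| 3 Single copy assay | Yes | Rank-sum on change |
| 4 CD4+ count | Yes | Rank-sum on change |
| 5 Cell-associated RNA and DNA | Yes | Rank-sum on change |
| 6 Neuropsychological battery | **No** | Longitudinal comparison of individuals; no test |
| 7 Hospitalization, non-AIDS conditions | Yes | Rank-sum; exact unconditional test |

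Item 6 has the structure of items 3 to 5 but lacks their last sentence.

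**2. Inputs for an illustration**

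The SAP states no arm size, practice gain, retest correlation or within-person test for this endpoint, so there is no planned figure to reproduce. From the SAP: two-sided testing at 0.05, and the rank-sum test on change (items 3 to 5). Assumed:

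- no treatment effect;
- the same gain *g* in both groups, 0.2 to 0.4 SD of the score;
- retest correlation *r* of 0.7 to 0.8;
- normally distributed change;
- 10, 15 or 20 participants in the within-person comparison;
- a signed-rank test as the within-person test.

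**3. Formula**

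For a score with SD 1 at both visits, the SD of change is √(2(1 − r)).

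- r = 0.7: √0.6 = 0.775. Standardised gain is 0.2/0.775 = 0.258 up to 0.4/0.775 = 0.516.
- r = 0.8: √0.4 = 0.632. Standardised gain is 0.2/0.632 = 0.316 up to 0.4/0.632 = 0.632.

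**4. Within-person test: share of trials reporting a change**

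Signed-rank test with exact critical values, 100,000 simulated trials per setting:

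| n | g = 0.2, r = 0.7 | g = 0.2, r = 0.8 | g = 0.4, r = 0.7 | g = 0.4, r = 0.8 |
|---|---|---|---|---|
| 10 | 10.9% | 14.3% | 30.1% | 42.0% |
| 15 | 14.5% | 19.5% | 43.9% | 59.7% |
| 20 | 18.7% | 25.7% | 56.9% | 74.3% |

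With no gain and n = 10 the rate is 4.8% to 4.9%, so the excess comes entirely from the assumed gain.

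Check by the non-central t distribution (paired t test), with non-centrality √n × standardised gain:

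- n = 10: 0.82 to 2.00, giving 11.3% to 43.1%;
- n = 15: 1.00 to 2.45, giving 15.4% to 62.5%;
- n = 20: 1.15 to 2.83, giving 19.5% to 76.5%.

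These agree closely with the simulated rates.

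**5. Between-group test on change**

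A gain common to both groups shifts both sets of changes equally, so the rank-sum null distribution is unaffected. Exact two-sided size:

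| Group sizes | Size |
|---|---|
| 5 v 10 | 4.00% |
| 10 v 10 | 4.33% |
| 15 v 15 | 4.53% |
| 20 v 20 | 4.91% |

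Simulated rates at gains of 0, 0.2 and 0.4 SD agree within 0.1 percentage point.

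**The case against.** The strongest reply is that the closing paragraph already supplies the missing rule. It covers continuous variables, uses the same weeks 24 and 48, compares change between groups by rank-sum test, and allows repeated measures models with a group effect. Its later sentences, on the 0.05 level and on multiplicity, read as applying to the whole trial. This reading is possible, and it means the plan for item 6 is ambiguous, not certainly within-person only. It does not settle the matter. The paragraph opens on exploratory objectives and says that these follow the secondary ones, item 6 does not refer to it, and items 3 to 5 state the rule in full without relying on it. Even on the generous reading, item 6's claim about longitudinal comparison would stand beside a different rule.

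It can also be said that the sentence merely justifies using two score scales and is permissive. The wording is permissive, but item 7 uses the same verb and still names groups and a test.

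The illustration uses a signed-rank test that the SAP does not contain, and every numerical input other than the 0.05 level is assumed. That is correct. The percentages show how far the reasoning can mislead; they are not a planned error rate.

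Finally, the intervention might include the interruption of ART. If both groups interrupt, a between-group comparison would cancel that effect. This is a good reason to define the term. It does not rescue the within-person inference, which cannot separate the interruption from retest learning and time either.

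**Conclusion.** The concern holds. Item 6 is the only secondary item without a stated between-group comparison, and the one comparison it describes cannot support the conclusion attached to it. At best the planned analysis is ambiguous.

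If a shared practice gain of the assumed size exists and a within-person test is used, the chance of reporting a change with no treatment effect is roughly two to fifteen times the nominal 5% (10.9/5 ≈ 2; 74.3/5 ≈ 15). The between-group test does not exceed 5%. That contrast rests on the gain being equal in both groups; the size of the inflation rests on the assumed gain, correlation and sample sizes. With no gain there is no inflation.

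The consequence is moderate. This is one of seven secondary endpoints in a study that treats its inferences as hypothesis generating. It should nevertheless be corrected, because the SAP calls this question the main interest of the neuropsychological testing.

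**What to change.** In SAP section 2, item 6, replace the sentence on longitudinal comparison with the one from items 3 to 5, "Change from baseline at week 24 and week 48 will be compared between treatment groups using a Wilcoxon-Rank Sum test", applied to each score (z-score, or raw score where no norms exist). Add that within-person trajectories are descriptive only. State whether the intervention means VRC01 alone or VRC01 together with the interruption of ART. If it includes the interruption, say that within-person change describes that period without isolating its effect. Adjustment for the week 0 score is optional.

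The cost is a short edit to one item, in wording the SAP already uses. No additional data, visits or tests are required.
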